SGR=22% vs Control=21%). We believe due to the high level of missing data and the intent to treat analysis we did not show a difference between interventions and these results need to be interpreted with caution. However, it is noteworthy that 75% of SGR participants who were quit at end of treatment remained quit at 6-months speaking to the sustainability of the SGR intervention. These results support the need to add an additional assessment at 3-months to determine the more proximal time to quitting.

Strengths of our pilot work include strong evidence of feasibility and acceptability of the intervention. The SGR group had an excellent response rate to the SGR texts (72%),

showing that smokeless tobacco users will interact with our intervention. Further, our self-report quit rates were promising and much higher in the SGR group (22% vs 9%, Cohen’s d equivalent=0.55, medium effect) in the short term, and these quit rates were sustained in the SGR group at 6-months; most chewers who quit at end of treatment remained quit at 6-months (75%). After critically evaluating our pilot work, we found areas for improvement for the current study (see Table 2). Thus, our pilot work found that a text-based SGR intervention is both feasible and acceptable among underserved smokeless tobacco users and warrants further testing. For the current study we have included an evidenced-based control condition to determine if our SGR intervention improves quit rates compared to an available evidenced-based cessation intervention. Results of this study will inform future treatment strategies in this population of tobacco users.

[figure not shown]
Overall Strategy

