A text-based reduction intervention for smokeless
tobacco cessation

NCT04315506

01/28/2022

Data Analysis Plan

We will use descriptive statistics to summarize the sample characteristics and study measures collected at baseline and longitudinally. We will perform non-directional statistical tests with the significance level set at 0.05 for all analyses. The primary outcome is self-report smokeless tobacco cessation at month 6 (Aims 1 & 3). Due to the exploratory nature of the mediator analyses, the significance level of 0.05 will not be adjusted for the multiple tests associated with steps for determining mediation (Aims 2 & 3). For the efficacy and mediator analyses we will perform, both intention-to-treat (ITT) and completers analyses. ITT analyses will be the primary analyses and will include all participants randomized to an intervention regardless of treatment or study completion. Completers analyses will include only those participants who complete the month 6 assessment, regardless of level of adherence to the SGR or control intervention. Effect sizes and 95% confidence intervals (CIs) will be reported to address clinical significance for the efficacy and mediator analyses. Analyses will be conducted by our faculty biostatistician [name] (Co-I) to ensure application of rigorous methods and implementation of quality assurance procedures. All data will be stored in REDCap at Duke University and downloaded to SAS Version 9.4 for the statistical analysis.

Handling of Missing Data. Missing smokeless tobacco cessation outcome data will be imputed as “did not quit” for the Aim 1 and 3 primary outcome analyses applying the ITT principle. Aim 2 will apply hierarchical mixed-effects trajectory models to assess change in withdrawal symptoms, craving, self-regulation and restraint. Trajectory methods will allow missing outcome data when estimating participant trajectories. To test the data missing at random (MAR) assumption of trajectory methods, intervention group differences in missing rate at each time point and number of missing values across time will be compared using tests for difference in proportion or cumulative counts. For missing covariate data in the models, imputation methods (e.g., multiple imputation) will be carefully applied as needed. The latter will be particularly important for the ITT analyses.

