will be evaluated separately (See **Figure 5**). First, the initial step of the formal mediation analysis will be to determine whether the intervention group significantly influences the trajectory of change in withdrawal symptoms, craving, self-regulation, and restraint (Path A). The Path A analysis will be completed in Aim 2. Second, logistic regression will be used to examine whether the slope coefficients for the individual trajectories of the proposed mediator are associated with cessation at 6 months (Path B). The final logistic regression model conducted for Aim 1 will be used to test for intervention group differences in cessation at 6 months post-intervention (Path C). Finally, the slope coefficients for the proposed mediator will be added as a covariate to the Path C logistic regression model (Path C'). The Path C' analysis will allow us to examine the effects of the intervention groups on Month 6 cessation after adjusting for the effects of change in the proposed mediator across time. For each proposed mediator of SGR effects, mediation will be established if the SGR group compared to the control group has significantly greater improvements in the mediator as an outcome (Path A), the degree of improvements in the mediator across time is related to cessation at 6 months (Path B), the SGR group has a significantly higher cessation rate at 6 months compared to the control group (Path C), and SGR effects on cessation are partially or fully diminished after adjusting for the mediator effect (Path C'). A Sobel's Test will be used to further determine the degree to which improvement in withdrawal, craving, self-regulation, and restraints mediate intervention effects. ORs and their 95% CIs will provide estimates of effect sizes.

Figure 5: Mediation Analysis Pathways

Statistical Power. The sample size of 500 (N=250 per intervention arm) will provide at least 90% power to address the primary aim (Aim 1), primary outcome (self-reported cessation at 6 months), and primary analysis (ITT analysis). A previous smokeless tobacco SGR study in smokeless tobacco resulted in a 27% cessation rate at 6-months.²⁵ Our pilot resulted in a 22% cessation rate at 6-months. Given the improvements to our

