SGR intervention, we conservatively estimate a slightly higher quit rate at 25% at 6-months. The Enough Snuff Control intervention has yielded quit rates between 16-18% at 6-months;^{43,44} however, these studies were clinic-based and deployed out of dental offices with military personnel, representing a different population and mode of delivery than we are proposing. A similar, web-based version of the intervention delivered remotely yielded quit rates of 12%.³⁰ Given the low-touch remote nature of our study and the focus on rural and underserved populations, we expect quit rates in the control group to be closer to 12% at 6-months. Therefore, we estimate a medium effect at 6-months. In summary, the target sample size is based on the assumptions that: (1) logistic regression will be performed with two-tailed significance set at 0.05; and (2) the quit rate at month-6 may be as low as 25% in the SGR group and 12% in the control group at 6-months for the ITT analysis (odds ratio of 2.44, Cohen's *d* equivalent of 0.493, approximate medium effect); Consistent with prior smokeless intervention studies, the target sample size will not be adjusted for attrition rate and dropouts will be coded as continued to use. Based on these assumptions, a sample size of 250 per arm will provide 96% power to test the primary aim. If an attrition rate of 30%

is observed in each arm of the proposed study, the resulting sample size of 175 per arm will provide at least 80% power for the completers analysis for Aim 1.

Addressing scientific rigor and reproducibility. All final study procedures will be documented in detail with accompanying scripts, documents, examples and measures. Our assessments and reports will include descriptive statistics. The study PI will oversee the training of study staff and make sure all procedures meet high standards of fidelity using a checklist of key tasks with periodic observations of performance of tasks. Facebook recruitment quality control will be maintained by [name] with consultation from [name]. Texting quality control standards will be maintained under the supervision of [name]. [name] will oversee quality control of all assessment measures during the study. Further, the study statistician, [name], will document data quality control standards and procedures (e.g., data checking).

Potential Risks and Challenges

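### Exploratory Aim 3 can declare a mediator established only if the total month-6 cessation difference is also significant, so Path C power caps the chance of declaring a real one

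*SAP*

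**What the plan says.** In the SAP, under Exploratory Aim 3 Statistical Analysis, each of four mediators (withdrawal, craving, self-regulation, restraint) is assessed separately. Mediation counts as established when four conditions, joined by *and*, are met:

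- Path A: SGR improves the mediator significantly more than control does.
- Path B: the participant's mediator slope is related to month-6 cessation. No adjustment for arm is mentioned.
- Path C: "the SGR group has a significantly higher cessation rate at 6 months compared to the control group (Path C").
- Path C': the arm effect shrinks once the mediator slope is added to the Path C model.

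The Sobel test follows, to gauge the degree of mediation. It is not offered as another way to establish it. Path C uses the final Aim 1 logistic model, so it is the primary comparison again. Nothing says how mediation could be declared if Path C is not significant.

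The opening of the Data Analysis Plan says "We will perform non-directional statistical tests with the significance level set at 0.05 for all analyses". It also calls the mediator analyses exploratory, leaves them unadjusted for multiplicity, and promises effect sizes and 95% CIs for them. No CI for the indirect effect itself is specified.

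**The concern.** Aim 3 asks whether SGR changes a mediator and whether that change carries over to quitting. This is the indirect effect, built from Path A and the mediator-cessation path with arm held fixed. Path C tests a different null hypothesis, that the total arm difference is zero. The total is the indirect effect plus everything else SGR does. A real indirect effect can sit inside a total too small to reach significance, or be offset by a path in the opposite direction. In either case the rule usually returns *not established*, however clear the mediator data are.

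At stake is the trial's conclusion about mechanism after a modest or null primary result, when evidence on what SGR did and did not change would be most useful for later work.

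**Working it through.** **Inputs from the documents.** Two-sided 0.05 (SAP, Data Analysis Plan). From SAP, Statistical Power: "The sample size of 500 (N=250 per intervention arm"), and "the quit rate at month-6 may be as low as 25% in the SGR group and 12% in the control group at 6-months". Alternative control rate, same section: "The Enough Snuff Control intervention has yielded quit rates between 16-18% at 6-months". The SGR pilot rate of 22% is also there. The pilot's 6-month intention-to-treat result is in the Protocol's account of the pilot: "SGR=22% vs Control=21" (per cent).

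**Step 1: reproduce the plan's figures.** The SAP gives "odds ratio of 2.44, Cohen's *d* equivalent of 0.493, approximate medium effect".
- OR = (0.25/0.75)/(0.12/0.88) = 2.44; d = ln(2.444) × √3/π = 0.493. Both agree.
- Power = Φ[(Δ − 1.96·s0)/s1], where s0 = √(2p̄(1−p̄)/n) and s1 = √((p1(1−p1) + p2(1−p2))/n).
- With p̄ = 0.185 and n = 250, s0 = 0.03473 and s1 = 0.03424. Then (0.13 − 0.0681)/0.03424 = 1.81, and Φ = 96.5%.

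The SAP says "a sample size of 250 per arm will provide 96% power to test the primary aim", which agrees.

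**Step 2: the cap.** Because the conditions are joined by *and*, P(established) ≤ P(Path C significant in favour of SGR). No mediator assumption is needed. The same formula at other rates in the documents, without covariates, gives:

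| SGR vs control | Path C power, 250 per arm |
|---|---|
| 25% vs 12% (planned) | 96.5% |
| 22% vs 12% | 85% |
| 25% vs 16% | 70% |
| 25% vs 18% | 48% |
| 22% vs 16% | 40% |
| 22% vs 18% | 20% |
| 22% vs 21% (pilot) | 4.6% favouring SGR; 5.9% counting either direction |

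Where direct and indirect effects cancel exactly, the cap is 2.5%.

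**Step 3: how much of a real mediator is lost.** The documents give no mediator effect sizes, so these are assumed. The simulated mediator is a normal score shifted by *a* SD in the SGR arm; the log-odds of quitting rise by *b* per SD; the direct effect is set to give the stated quit rates. There were 1,500 to 2,000 trials per scenario with 250 per arm. The alternative rule requires Path A and the arm-adjusted mediator path to be significant. Ranges are across repeated runs.

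| Rates | Written rule, a=0.4, b=0.8 | Written rule, a=0.3, b=0.6 |
|---|---|---|
| 25% vs 12% | 96–97% | 88–89% |
| 25% vs 18% | 47–49% | 45–47% |
| 22% vs 16% | 39–40% | 38–39% |
| 22% vs 18% | 18–22% | 18% |
| 22% vs 21% | 4–6% | 4–5% |

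The alternative rule detects the stronger mediator in about 99% of trials and the weaker in about 91–92%. With a=0.4, b=0.7 and control at 12%:
- Fully mediated effect (SGR 15.1%): alternative 99%, written rule 17%.
- Indirect effect cancelled by an opposing direct effect (SGR 12%): alternative 99%, written rule 2.3%.

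**Step 4: false declarations.** Here Path A is real but the mediator has no effect on cessation.
- *No shared cause of mediator and cessation.* The alternative rule fires, in the beneficial direction, in about 2–3% of trials per mediator (about 5% counting either direction). The written rule fires in 0.2% at 16% vs 16%, but in 10% at 25% vs 12%, because its Path B is not arm-adjusted and picks up the arm effect.
- *A shared cause* (assumed log-OR 0.8 on cessation, correlation 0.3–0.5 with the mediator). At 16% vs 16% the alternative rule fires in 43–86% and the written rule in 1–3%. At 22% vs 21% the figures are 52–90% and 3–4%. At 25% vs 12% they are 43–89% and 69–93%.

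**The case against.** The strongest reply has four parts.

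*The condition fits the question as worded.* The Protocol and SAP ask what mediates the intervention's effect on cessation, so requiring that effect is coherent and follows the framework the SAP names. This stands as far as it goes: the rule is openly stated and is not an internal contradiction. It still gives a wrong negative when a real indirect effect lies within a modest or offset total.

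*Nothing is switched off.* A reader might infer that a non-significant Path C ends the mechanism analysis, or that the mediators would be reported as having failed. The SAP does not support that. Path A is Aim 2 and is reported in its own right; Path B, Path C' and the Sobel test carry no stated dependence on Path C. Only the word *established* is withheld.

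*The condition guards against false claims.* A reader might infer that removing it costs nothing in error. That holds only without mediator-outcome confounding. The mediator slope runs from baseline to month 6 and the outcome is 7-day use reported at month 6, so shared causes or reverse causation are plausible. With a null total effect, Path C then does block many spurious declarations. But it is not a control for confounding: at the planned rates the written rule misfires more often than the alternative.

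*The low-power scenarios are not the plan's.* This is correct. The SAP sets aside 16–18% with reasons (dental clinics, military personnel). The pilot used a four-week programme, a different control and 33 controls, and the Protocol urges caution over its missing data. The caps show sensitivity and do not forecast the trial.

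**Conclusion.** The point holds in limited form. The declaration of mediation is capped by Path C power. The loss is about 3 points at the planning rates, and large if the true difference is nearer the other rates the documents cite. The caps rest only on document rates and a two-proportion calculation; covariates in the final Aim 1 model could move them somewhat. The detection and false-declaration rates also rest on assumed mediator and confounder strengths, and on a single score standing in for the estimated slope.

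The consequence is confined to an exploratory aim. The primary test, sample size and component analyses are unaffected. It is still worth correcting before analysis, because the rule decides what the trial may say about mechanism and its answer depends on a different hypothesis from the one Aim 3 poses.

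**What to change.** In Exploratory Aim 3 of the SAP:

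1. Remove Path C significance from the definition of mediation.
2. Judge each mediator on Path A and on the mediator coefficient adjusted for arm. The Path C' model already supplies that coefficient.
3. Report the indirect effect with its 95% CI (for example by bootstrap) whatever Path C shows, with the total effect alongside, and label any indirect effect found without a significant total effect.
4. Describe the result as associational and exploratory, since the mediator is not randomised and its slope ends at the outcome visit. Limit any statement about error control to the case of no mediator-outcome confounding, and note that four mediators are tested without adjustment.

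The change is to wording and reporting and needs no new data. Its real cost is that, when the total effect is null, confounding can produce an apparent indirect effect that the present rule would usually have left undeclared. Item 4 is therefore a necessary part of the change.

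### Aim 3 gauges mediation by Sobel's test, which is conservative, and by the fall in a logistic coefficient, which tends to understate the mediated share

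*SAP*

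**What the plan says.** The SAP section Exploratory Aim 3 Statistical Analysis evaluates withdrawal, craving, self-regulation and restraint one at a time. Mediation is called when four conditions hold together:

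- Path A: the arm changes the mediator's trajectory.
- Path B: the individual mediator slope is related to quitting at 6 months.
- Path C: SGR has the significantly higher quit rate.
- Path C': once the slope is added to the logistic model, "SGR effects on cessation are partially or fully diminished after adjusting for the mediator effect".

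After that rule, Sobel's "Test will be used to further determine the degree to which improvement in withdrawal, craving, self-regulation, and restraints mediate intervention effects". It is the only test of the indirect effect that the SAP names. The section also promises odds ratios with 95% CIs, but it plans no interval for the indirect effect itself, no rescaling of the logistic coefficients and no indirect effect on the risk scale.

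The opening of the SAP sets the error rates: "We will perform non-directional statistical tests with the significance level set at 0.05 for all analyses". It adds: "Due to the exploratory nature of the mediator analyses, the significance level of 0.05 will not be adjusted for the multiple tests". No power calculation is given for mediation.

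**The concern.** There are two separate problems.

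**Sobel's test.** It treats the product of the two path estimates as normal. That product is skewed when either path is modest, so the test rejects too seldom. It also yields a z value, which is not a measure of degree.

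**C against C'.** These are arm coefficients from logistic models with different covariates. Adding a strong predictor of quitting moves the arm log odds ratio away from zero even without confounding (non-collapsibility). This works against the fall that mediation produces. The before-and-after comparison therefore tends to show too little mediation, and in some cases the coefficient rises although mediation is real.

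At stake is what the trial reports about mechanism, which the protocol (Significance and Innovation) puts forward as a contribution to later treatment strategies. A real pathway could be reported as weaker than it is, or as unsupported.

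**Working it through.** **Inputs from the SAP, Statistical Power.** Quit rates: "the quit rate at month-6 may be as low as 25% in the SGR group and 12% in the control group". Sample size: 250 per arm, or 175 per arm with 30% attrition. Test: two-sided 0.05.

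**Inputs assumed, because the documents give none.** Arm effect on the mediator a = 0.2 to 0.4 SD. Mediator effect on quitting b = 0.3 to 1.5 log odds per SD. The mediator slope is treated as one normal variable measured without error, and Path B is adjusted for arm (the SAP does not say whether it is).

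**Step 1: reproduce the plan's figures.** OR = (0.25/0.75)/(0.12/0.88) = 2.444, so the marginal arm coefficient is c = ln 2.444 = 0.894, and d = 0.894 × √3/π = 0.493. This matches "odds ratio of 2.44, Cohen's *d* equivalent of 0.493, approximate medium effect". A two-proportion calculation gives 96.5% power at 250 per arm and 88.3% at 175, consistent with "a sample size of 250 per arm will provide 96% power to test the primary aim" and with the stated minimum of 80% for completers.

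**Step 2: Sobel's test.** z = zA·zB/√(zA² + zB²). If the two paths are equally strong this is zA/√2, so each path must reach 1.96 × √2 = 2.77 instead of 1.96. When each path has 80% power, both are significant together in 0.8 × 0.8 = 64% of trials, whereas Sobel's test rejects in 41%, a loss of 23 points. When each path has 99% power the loss is 2 points.

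Simulation at 250 per arm (1,500 trials per row, marginal quit rates held at 12% and 25%):

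| a (SD) | b (log odds per SD) | Sobel | A and B both significant | Product-distribution CI |
|---|---|---|---|---|
| 0.25 | 0.4 | 53% | 74% | 73% |
| 0.3 | 0.3 | 43% | 66% | 64% |
| 0.3 | 0.5 | 82% | 90% | 90% |
| 0.3 | 1.0 | 89% | 92% | 92% |
| 0.4 | 0.75 | 99% | 100% | 100% |

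Over the whole grid the loss against joint significance is 0 to 23 points at 250 per arm and 1 to 25 at 175. The largest is at 175 per arm with a = 0.3 and b = 0.4: Sobel 39%, joint 64%, product CI 62%. When the arm has no effect on the mediator, Sobel's test rejects in 1.1% of trials and the product interval in 4.5%. Monte Carlo error is about 1 to 1.5 points per cell.

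**Step 3: does this reach the four-part rule?** With a mediator odds ratio of 1.5 per SD and a = 0.2 SD, Sobel's test has 37% power, the product interval 54% and the four-part rule 54%. With a = 0.3 SD the figures are about 70%, 84% and 84%.

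**Step 4: the fall from C to C'.** Model: M = a·G + N(0,1); logit P(quit) = i + c'·G + b·M, with i and c' solved so that the marginal quit rates are 12% and 25%. Take b = ln 3 = 1.099 and a = 0.2.

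- c' = 0.828. The fall is (0.894 − 0.828)/0.894 = 7.4%.
- Giving control participants the SGR mediator distribution raises their quit rate by 2.2 points, which is 17% of 13 points (pure indirect effect).
- Giving SGR participants the control mediator distribution lowers theirs by 3.3 points, which is 25% of 13 points (total indirect effect).
- On the log-odds scale, a·b = 0.2 × 1.099 = 0.220, and 0.220/(0.220 + 0.828) = 21%.

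With a = 0.1 the coefficient rises 4.9%, while 8% to 13% of the risk difference is mediated. Over the a = 0.2 to 0.4 grid, C − C' recovers between 9% and 90% of a·b. For a weaker mediator (odds ratio 1.5, a = 0.2) the distortion is small: c' = 0.834, a fall of 6.7%, against 8.9% on the log-odds scale and 7% to 11% of the risk difference.

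**Step 5: cost of the criterion as a yes/no rule at 250 per arm** (four-part rule against A, B and C alone):

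- a = 0.3, b = 1.0: 88% against 89%.
- a = 0.2, odds ratio 3: 56% against 59%.
- a = 0.2, b = 1.5: 47% against 59%.

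**The case against.** The strongest reply is that the rule which decides mediation is not Sobel's test. The four conditions already contain the tests of A and B, and in the modest-path scenarios they match the product interval (Step 3). This stands. A reader might infer that the plan gives up some 20 points of power and will miss modest mediators. The documents do not support that: Sobel's test comes after the rule, nothing makes it a gate, and the size of its loss depends on mediator effects that are stated nowhere. With an odds ratio of 3 and a = 0.2 SD the loss is only 3 to 4 points.

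A second reply is that the two harms do not coincide. Sobel's test loses most with weak mediators, where the coefficient falls much as it should; the shrinkage is most distorted with strong mediators, where Sobel's test loses little. This also stands. The rising coefficient is a corner case: at a = 0.1 SD, zA = 0.1/√(2/250) = 1.12 and Path A has about 20% power, so any method would seldom detect that mediator.

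A third reply is that a percentage fall in log odds and a share of a risk difference are on different scales, and that the SAP promises no proportion mediated. The scale point is fair, but the 21% against 7% in Step 4 is on the log-odds scale throughout and shows the same direction. As to the promise, the SAP's criterion itself distinguishes partial from full reduction, which invites readers to compare the two odds ratios as a measure of degree.

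**Conclusion.** The concern holds as a minor point about how the degree of mediation is measured in an exploratory aim.

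- Sobel's test is conservative. Its power is about 0 to 25 points below that of better-behaved tests of the indirect effect, under assumed mediator effects, and the loss is largest when both paths are modest. This weakens the reported test of the indirect effect. It affects whether mediation is called only if Sobel's test is treated as a further gate, which the SAP leaves open.
- The fall from C to C' understates mediation: slightly for weak mediators, materially for strong ones (7% against 17% to 25% of the risk difference in the example, depending on how the indirect effect is defined).
- As a yes/no condition the C' criterion usually costs little, because it sets no threshold. The clear loss is for a strong mediator on which the arm has a small effect.

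It would go too far to say that a fixed amount of power is lost in this trial or that real mediators will generally be missed. The figures rest on a single error-free normal mediator and on assumed values of a and b. Aim 1, its power and the sample size are untouched.

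**What to change.** In Exploratory Aim 3, replace Sobel's test, and the C against C' comparison as the measure of degree, with one estimate per mediator: the indirect effect as a difference in quit probability, standardised over the sample. Give it a percentile bootstrap 95% CI that resamples participants within arm and refits both stages (the mixed model that supplies the slopes and the logistic model). State which definition of the indirect effect is used, since the two differ (17% against 25% in the example).

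Keep Paths A, B and C as described. Do not require a fall in the logistic coefficient for mediation to be called. If the sponsor prefers to keep Sobel's test, the SAP should say whether it decides anything.

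The cost is SAP wording, a short program and more computing: four mediators in two analysis sets (ITT and completers) make 4 × 2 = 8 mixed-model fits per resample. No new data are needed.
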